### 4.1.3 Hypothesis

Primary outcome

*NP HCP vs OP+N HCP*

H0:  $\mu_e - \mu_s \leq -d \rightarrow \mu(\text{NP HCP ct}) - \mu(\text{OP+N HCP ct}) \leq -3$

H1:  $\mu_e - \mu_s > -d \rightarrow \mu(\text{NP HCP ct}) - \mu(\text{OP+N HCP ct}) > -3$

*OP+N HCP vs OP+N GSS*

H0:  $\mu_e - \mu_s \leq -d \rightarrow \mu(\text{OP+N HCP ct}) - \mu(\text{OP+N GSS ct}) \leq -3$

H1:  $\mu_e - \mu_s > -d \rightarrow \mu(\text{OP+N HCP ct}) - \mu(\text{OP+N GSS ct}) > -3$

*OP+N HCP vs OP+N USS*

H0:  $\mu_e - \mu_s \leq -d \rightarrow \mu(\text{OP+N HCP ct}) - \mu(\text{OP+N USS ct}) \leq -3$

H1:  $\mu_e - \mu_s > -d \rightarrow \mu(\text{OP+N HCP ct}) - \mu(\text{OP+N USS ct}) > -3$

Secondary outcome:

We will stratify the primary outcome by viral load (low, medium, high).

### 4.1.4. Statistical test

A variant of a paired student t test or Wilcoxon test (if non-normal distribution) with exchange of null and alternative (relaxed) hypotheses will be used as a non-inferiority test to assess differences in cycle threshold (Ct, considered as a log2-transformed measure of the amount of viral RNA load) between the NP and OP/N samples (HCP and GSS). Stratification for possible confounders will be done using logistic regression.

In order to show agreement between the approaches and estimate the limits of agreement and those are not too large, different graphical methods, such as Bland Altman diagrams will be used to show agreement between the approaches.

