## GLOSSARY OF ABBREVIATIONS

AES	Advanced Encryption Standard
BASEC	Business Administration System for Ethical Committees
CRF	case report form
Ct	cycle threshold
EBPI	Institut für Epidemiologie, Biostatistik und Prävention
FOPH	Federal Office of Public Health
GSS	guided self-sampling
H0	null hypothesis
H1	alternative hypothesis
HCP	healthcare professional
HRA	Human Research Act
HRO	Ordinance on Human
NP	nasopharyngeal
OP+N	oropharyngeal and nasal
PCR	polymerase chain reaction
RT	realtime
SD	standard deviation
SOP	standard operating procedure
TLS	Transport Layer Security
USS	unsupervised self sampling
VOC	variant of concern
μs	mean in the standard treatment group
μe	mean in the experimental treatment group
d	non-inferiority limit

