#### 4.1.2 Sample size

The SD of the mean of Ct values for RT-PCR analysis of multiple samples is not clearly defined in the literature and varies between studies.

If there is truly no difference between the standard and experimental treatment, then 85 patients per group are required to be 90% sure that the lower limit of a one-sided 97.5% confidence interval (or equivalently a 95% two-sided confidence interval) will be above the non-inferiority limit of -3.

We, therefore, estimated a standard error of six that accounts for this variance. In addition, the limit of non-inferiority was set at three according to clinical significance.

Results will be stratified by symptom status, age, and sex.

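### The fallback to a Wilcoxon test under non-normality lets the data decide whether the mean or the pseudo-median Ct difference is held against the 3 Ct margin

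*Combined protocol and SAP*

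**What the plan says.** The glossary defines the two symbols in the hypotheses as the "mean in the experimental treatment group" and the "mean in the standard treatment group". Section 4.1.3 states three non-inferiority hypotheses, each as a difference of mean Ct against -3: nasopharyngeal (NP) HCP vs oropharyngeal plus nasal (OP+N) HCP, OP+N HCP vs guided self-sampling (GSS), and OP+N HCP vs unsupervised self-sampling (USS).

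Section 4.1.2 says that "the limit of non-inferiority was set at three according to clinical significance". It sizes the trial so that the "lower limit of a one-sided 97.5% confidence interval" clears that limit, and concludes that "85 patients per group are required to be 90% sure".

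Section 4.1.4 names the test: a paired t test, or a "Wilcoxon test (if non-normal distribution) with exchange of null and alternative (relaxed) hypotheses". It does not say how normality is judged, whether raw Ct values or paired differences are checked, what quantity the Wilcoxon version estimates, or whether 3 Ct is still the right limit for that quantity. No other section makes the mean difference decisive again.

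**The concern.** The margin was set for a mean. A signed-rank test shifted by 3 Ct asks whether the pseudo-median of the paired differences is above -3. For symmetric differences the two questions coincide; for skewed differences they need not. The switch operates when the distribution looks non-normal, and skew is one way for that to happen, so the estimand can change in the very data where the change matters.

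Section 2.2 treats Ct as a surrogate for sampling quality, so a poor self-swab shows as a higher Ct. If a minority of self-swabs are poor, HCP minus self-swab has a long negative tail. The tail pulls the mean down more than the pseudo-median and can itself cause the switch. A mean deficit at or beyond 3 Ct could then be declared non-inferior. If the tail lies in the HCP swabs, the reverse happens and true non-inferiority is harder to show. In both cases the deciding test would be settled after seeing the data.

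**Working it through.** **1. The stated sample size rests on a mean.** Inputs from 4.1.2: margin 3, variability 6 (called a standard error, but it works only as an SD), true difference 0, one-sided 2.5%, power 90%.

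n per group = 2 × 6² × (1.960 + 1.282)² / 3² = 2 × 36 × 10.51 / 9 = 84.1, rounded up to 85. This reproduces the plan's figure; power at 85 is 90.3%. The formula is for two independent means.

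**2. What the documents leave open.** The SD of paired differences is not given. If 6 is the SD of a single sample, the SD of a difference is 6√(2(1-ρ)), where ρ is the within-person correlation: 8.5 at ρ = 0, 6.0 at ρ = 0.5, 4.2 at ρ = 0.75, 2.7 at ρ = 0.9. Values from 3 to 8.5 are therefore worth examining. The share and severity of failed swabs are also not given.

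**3. How far mean and pseudo-median separate.** Let D = HCP Ct minus self-swab Ct. Suppose unaffected pairs are centred at 0 and a share p is shifted down, so that the mean is -p × shift = -3 throughout.

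| Failed self-swabs | SD | Mean | Pseudo-median |
|---|---|---|---|
| 10% by 30 Ct | 3 | -3 | -0.63 |
| 20% by 15 Ct | 3 | -3 | -1.64 |
| 20% by 15 Ct | 6 | -3 | -2.49 |
| 30% by 10 Ct | 3 | -3 | -2.72 |
| 40% by 7.5 Ct | 3 | -3 | -2.93 |

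The gap is wide for few, severe failures and narrow for frequent, mild ones.

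**4. False declarations of non-inferiority.** Simulation of 85 pairs with the true mean exactly at -3 and one-sided 2.5% tests. The switch is modelled as Shapiro-Wilk p<0.05 leading to Wilcoxon (an assumption, since the plan names no rule). 10% or 20% of self-swabs fail by 10 or 15 Ct; the centre of the other pairs is set so that the overall mean is -3.

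| SD of the other paired differences | t test or Wilcoxon by the switch |
|---|---|
| 3 | about 14-47% |
| 4 | about 7-20% |
| 6 | about 4-7% |
| 8.5 | about 3% |

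The t test used throughout gives about 2-4%.

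Beyond the margin: with 20% failing by 20 Ct (SD 3, unaffected pairs centred at 0) the true mean is 0.2 × (-20) = -4.0. Wilcoxon still declares non-inferiority in 33.0% of trials, the t test in 0.3%.

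**5. Checks.**
- Symmetric normal differences centred at -3: t 2.4%, Wilcoxon 2.1%.
- Symmetric heavy tails: t 2.4%, Wilcoxon 2.7%.
- Tail in the HCP swabs (10% by 10 Ct, SD 3, mean -3): t 1.8%, Wilcoxon 0.2%. The bias reverses.
- How often the switch operates: for failures at SD 3, in 94-100% of trials with 10-30% failing (10-30 Ct); at SD 6, in 54% with 20% failing by 15 Ct and 11% with 30% failing by 10 Ct.

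**The case against.** The mismatch between 4.1.3 and 4.1.4 is hard to dispute; its size and direction can be disputed, and much of that stands.

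- A reader might infer that the switch always works in favour of self-sampling. The documents do not support this. Any non-normality can trigger it, and a tail in HCP swabs makes it conservative. One of the three comparisons (NP HCP vs OP+N HCP) has no self-swab at all, and section 2.1 itself expects that NP sampling often cannot be done correctly.
- A reader might take a false-positive rate near 20% as the size of the problem. That figure needs an SD of about 4 and failures of 15 Ct. At SD 6, the only variability figure in the plan, the rate is 4-7%. Yet 6 does not settle the matter, because it is not stated to be the SD of paired differences, and the tail itself adds variance. With SD 3 and 25% failing by 12 Ct, the overall SD is √(9 + 0.25 × 0.75 × 144) = 6.0, and the rule gives 14.0% against 3.2% for t.
- No passage says that failed self-swabs are the usual source of non-normality, and Shapiro-Wilk is not the plan's stated rule.
- The t test is not exact under strong skew: it reaches 5.4% when 10% fail by 30 Ct.
- Eighty-five usable pairs are not assured for viral genes, because section 3.1 enrols people regardless of symptoms.
- The Bland-Altman plots in 4.1.4 would show a tail, but they decide nothing.

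**Conclusion.** The concern holds in this form: the plan sets its hypotheses, margin and sample size on mean Ct differences, then lets an unspecified normality judgement replace the mean by the pseudo-median against the same 3 Ct. That follows from the text alone.

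The consequence ranges from negligible to serious. Under the assumptions in step 4, the chance of declaring non-inferiority at the margin runs from about 3% (SD 8.5) to about 47% (SD 3), against about 2-4% for the t test. It is largest for a tight core of differences with a few badly failed self-swabs, and it reverses if HCP swabs carry the tail.

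Two limits apply. If failed swabs yield no Ct and their pairs are dropped, neither test sees the failures, and section 4.2 has no rule for this. Section 2.2 lists antigen concordance as primary and Ct as secondary, whereas 4.1.3 labels the Ct comparison primary. This affects how much weight the point carries, not whether it is right.

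**What to change.** In 4.1.4, delete the normality-dependent choice. State that, for each of the three comparisons in 4.1.3, non-inferiority is judged only from the two-sided 95% CI for the mean paired Ct difference against the 3 Ct limit, whatever the distribution. Name the interval in advance: t-based, or bootstrap if marked skew is expected, given the t test's slight excess above 2.5% there. Report the Wilcoxon test with the Hodges-Lehmann estimate and its interval as a sensitivity analysis, and comment on any disagreement, since it signals skew.

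In the same edit, say in 4.2 how a swab without a detectable Ct enters the paired analysis, and reconcile the primary endpoint between 2.2 and 4.1.3.

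The main change costs only wording: no extra participants or swabs. The statistical price is slightly less power than Wilcoxon when differences are symmetric with heavy tails.

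### The plan assigns confounder handling to logistic regression, which cannot give an adjusted or stratified Ct difference on the scale of the 3 Ct margin

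*Combined protocol and SAP*

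**What the plan says.** Section 4.1.4 plans a paired t test, or a Wilcoxon test if the data are not normal, with a shifted null, as a "non-inferiority test to assess differences in cycle threshold". The next sentence reads: "Stratification for possible confounders will be done using logistic regression". It names no dependent variable.

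Section 4.1.3 lists three comparisons under the primary outcome: NP HCP with OP+N HCP, OP+N HCP with GSS, and OP+N HCP with USS. Each is a difference in mean Ct tested against -3. Section 4.1.2 gives the source of that value: "the limit of non-inferiority was set at three according to clinical significance". The same section adds: "Results will be stratified by symptom status, age, and sex".

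Section 2.2 names a binary primary endpoint, antigen concordance, and lists the Ct comparisons as secondary. The possible confounders are in Shell Table 1 of the Appendix: age, sex, mobility impairment, occupation, socioeconomic status and education. Symptom status is not in that table.

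**The concern.** The only outcome in that paragraph of section 4.1.4 is Ct, which is continuous and measured by several methods in the same person. Logistic regression models a binary or categorised outcome and reports odds ratios. Read in sequence, the section asks a method that cannot produce a Ct difference to adjust an analysis of Ct differences.

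What is at stake is whether the adjusted and stratified results can support the non-inferiority conclusion. A reader will want to know whether the difference stays within 3 Ct after allowing for symptom status, age and sex, and whether it does so in each stratum. The stated method cannot answer that. It also leaves an analyst to choose an outcome, and perhaps a Ct cut-off, after the data are in.

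**Working it through.** **1. Inputs.** From section 4.1.2: margin 3 Ct, variability 6, one-sided 2.5% level, 90% power, true difference 0, 85 per group. From section 4.1.4: logistic regression for confounders.

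**2. The plan's own figure.** For two independent means, n per group = 2 × [SD × (z0.975 + z0.90) / margin]² = 2 × [6 × (1.960 + 1.282) / 3]² = 84.06, rounded up to 85. Power at 85 is Φ(3 / (6 × √(2/85)) − 1.960) = 90.3%. The figure reproduces if the 6 is read as an SD. Read literally as a standard error, it gives Φ(3/6 − 1.960), about 7%. The logistic regression sentence enters none of this, so the 85 does not depend on it.

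**3. Can the margin be moved to the odds-ratio scale?** This step is hypothetical, because the plan sets no cut-off. Assume normal Ct with SD 6, and let p be the share of reference samples below a cut-off. A rise of 3 Ct moves that share to p′ = Φ(z_p − 3/6), and the odds ratio is [p′/(1 − p′)] / [p/(1 − p)].

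| Reference share below cut-off | Share after +3 Ct | Odds ratio |
|---|---|---|
| 10% | 3.7% | 0.35 |
| 50% | 30.9% | 0.45 |
| 90% | 78.3% | 0.40 |

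With the cut-off at the median and the SD varied, the odds ratio is 0.19 at SD 3 and 0.55 at SD 8. The same 3 Ct therefore has no single odds-ratio equivalent. Any conversion needs a cut-off and a distribution that the plan does not state.

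**4. Does a linear model give the right quantity?** A standard logistic routine rejects values on the Ct scale, because its outcome must lie between 0 and 1. A linear model was fitted to 85 simulated within-person differences (true mean 0, SD 6), with centred age and sex. It returned an adjusted mean difference of -0.43 Ct, 95% CI -1.70 to 0.83. The numbers are only illustrative, but that lower limit can be set directly against -3.

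**5. The sections side by side.** Sections 4.1.2 to 4.1.4 contain no dichotomy of Ct, no margin on an odds-ratio or risk-difference scale, and no hypothesis or test for antigen concordance. There are two possible readings:
- The logistic model is for Ct. It then misses the scale of the hypotheses.
- The logistic model is for antigen results. Ct then has no adjusted model, and the stratified Ct results have no stated method.

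Both readings need a correction.

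**The case against.** The strongest reply is that section 4.1.4 never says the logistic model will be fitted to Ct; that comes from the order of the sentences. Antigen concordance is binary and is the endpoint that section 2.2 calls primary, and logistic regression suits it. This reading is possible. It does not remove the problem, because it leaves Ct, the scale of every stated hypothesis, without an adjusted analysis.

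A second reply is that little depends on adjustment. The three comparisons in section 4.1.3 are within-person, so fixed traits such as age, sex and education cannot confound them; they can only modify the difference. GSS versus USS is randomised. This stands, and it limits the weight of the point.

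A third is that ordinal logistic models exist and section 4.1.3 mentions low, medium and high viral load. There, however, viral load is a stratifier and not an outcome.

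A reader might infer more than the documents support:
- **That Ct will be dichotomised and effective sample size lost.** No split is planned, and the 85 belongs to the unadjusted calculation.
- **That standard errors will ignore pairing.** The form of the logistic model is not specified. A concordance outcome with one value per participant would raise no such problem.
- **That GSS versus USS fails for want of a comparison with 3 Ct.** Section 2.1 makes it a superiority question, so the margin does not apply. Sections 4.1.3 and 4.1.4 give it no hypothesis or test, which is a separate gap.

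**Conclusion.** The point holds, with limited reach. As written, the plan yields no adjusted or stratified Ct difference to compare with the 3 Ct limit, whichever outcome the logistic model was meant for. The unadjusted paired tests and the 85 per group stand as they are. This should be corrected, but it does not threaten the main test.

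That a logistic model cannot report a mean Ct difference needs no assumption about the data. The odds-ratio ranges do: they assume normal Ct and, for 0.35 to 0.45, an SD of 6. They show that the margin has no fixed translation and are not estimates of any loss in this trial.

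**What to change.** Amend section 4.1.4 to name the dependent variable of each model.

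- **Ct, non-inferiority comparisons.** Replace logistic regression with a linear model of the within-person Ct difference, in the direction of section 4.1.3, or a linear mixed model with sampling method as a fixed effect and participant as a random effect. In the mixed model, include method-by-covariate terms for symptom status, age and sex. In the difference model, the covariate coefficients already serve that purpose. Report adjusted and stratum-specific mean differences with 95% CI against the 3 Ct limit. Add the other Shell Table 1 variables as supporting analyses.
- **Ct, GSS versus USS.** Compare the within-person difference, self-sample minus HCP OP+N, between arms in a linear model, as a superiority question without a margin. State the assumption that the arm does not affect the HCP swab, which section 2.3.2 places after the self-swab.
- **Undetectable samples.** Section 3.1 admits people regardless of symptoms, so some will have no detectable viral Ct. State how these samples are handled; a plain linear model does not deal with them.
- **Antigen results.** Keep logistic regression only for antigen positivity or concordance, in conditional or clustered form where samples are paired.
- **Data capture.** Confirm that the CRF records symptom status. It is absent from Shell Table 1, and the CRF is not among the documents.

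The cost is SAP wording, plus one CRF item if symptom status is not yet captured. Sampling procedures and sample size do not change.

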### 4.2. Handling of missing data

Analysis is based on intention-to-treat assumption. Collected data until drop-out will be included for further analysis.

## 5 REGULATORY ASPECTS AND SAFETY

### 5.1 Local regulations / Declaration of Helsinki

This research project will be conducted in accordance with the protocol, the Declaration of Helsinki, the principles of Good Clinical Practice, the Human Research Act (HRA) and the Human Research Ordinance (HRO) as well as other locally relevant regulations. The Project Leader and the Sponsor both acknowledge their responsibilities.

### 5.2 Notification of safety and protective measures (HRA Art. 15, HRO Art. 20)

If, during the research project, circumstances arise which could jeopardize the safety or health of the participants or lead to a disproportionate relationship between the risks and burdens and the benefits, all the measures required to ensure protection are to be taken without delay.

The project leader is promptly notified (within 24 hours) if immediate safety and protective measures have to be taken during the conduct of the research project. The Ethics Committee will be notified via BASEC of these measures and of the circumstances necessitating them within 7 days.

### 5.3 Serious events (HRO Art. 21)

If a serious event occurs, the research project will be interrupted and the Ethics Committee notified on the circumstances via BASEC within 7 days according to HRO Art. 21.

### 5.4 Amendments

Substantial changes to the project set-up, the protocol and relevant project documents will be submitted to the Ethics Committee for approval according to HRO Art. 18 before implementation. Exceptions are measures that have to be taken immediately in order to protect the participants.

### 5.5 End of project

Upon project completion or discontinuation, the Ethics Committee is notified within 90 days. All biological materials and health-related data are anonymized upon the termination of data analysis.

### 5.7 Insurance

In the event of project-related damage or injuries, the Sponsor will be liable, except for damages that are only slight and temporary; and for which the extent of the damage is no greater than would be expected in the current state of scientific knowledge, except for claims that arise from misconduct or gross negligence. (Art. 12 HRO).

---

 A serious event is defined as any adverse event where it cannot be excluded, that the event is attributable to the sampling of biological material or the collection of health-related personal data, and which:

- a. requires inpatient treatment not envisaged in the protocol or extends a current hospital stay;
- b. results in permanent or significant incapacity or disability; or
- c. is life-threatening or results in death.

## 6 FURTHER ASPECTS

### 6.1 Overall ethical considerations

Already before the COVID-19 pandemic, the Swiss healthcare system has been undergoing a digital transformation. Digitalization enables decentralized living, e.g., in a home office, making life in remote areas more attractive. The desire for proximity to green nature, sufficient living space and a garden of one's own has continuously gained in importance. On the one hand, the population assesses Switzerland's healthcare system as particularly well equipped for digitalization; on the other hand, deficits in implementation are also perceived, especially in rural areas.

Rural areas of Canada, Finland, Ireland, Sweden, Scotland, Northern Ireland, Faroe Islands, Iceland, Greenland and Norway are also very positive about decentralized living. It allows progress, optimizes organization, and responds effectively to healthcare challenges with favorable economic outcomes. Similarities with Switzerland are that access to healthcare and schooling are capable of turning rural areas more attractive for young families to build resilience and encourage them to stay. This process is facilitated through digitalization. From a global perspective, digitalization of healthcare is on the rise, in keeping with increased testing capacities for COVID-19, which has proven essential to successful management of the pandemic.

In rural Australian areas, pending test results restrict everyday life. Emergency and family visits are denied in case of a pending COVID-19 test result and quarantine occurs when there is a suspected case of COVID transmission, while waiting for test results. Cumbersome testing is a global challenge especially in rural regions. Challenges comprise diagnostic insufficiency and low testing capacity since COVID-19 testing as well as treatment centers, are mainly situated in the urban areas. Lack of easily applicable testing capacity leads vulnerable groups to delay testing and seek medical care only at advanced stages of the disease, resulting in poorer outcomes. There is clearly a local and global desire for large-scale testing through fast, accurate and affordable diagnostic. A proven strategy to increase testing capacities is to foster public-private partnerships.

The use of self-testing with reactive antigen SARS-CoV-2 home tests is instrumental in enabling governments around the world to relieve some restrictions to a reasonable degree and open their economies and societies despite the advancing pandemic. Effective testing can also be critical during a rapid surge in cases, as evidenced in India and USA, with governmentally authorized reactive antigen SARS-CoV-home tests. Self-administered nasal swab rapid tests are on the rise and bring relevant profits worldwide in the healthcare sector such as less personnel effort, infrastructure, protective equipment and exposure of healthcare workers, healthy individuals and symptomatically ill individuals. This brings about not only positive impact on the health of each individual but also on a larger scale with advantageous social and economic outcomes.

The collected genetic study data will be handled as described above and the participants are not exposed to additional risks compared to standardized testing as described below. This, in keeping with the freely provided test-result and certificate suggests a fair balance for the study

participant, also from a public health and economic point of view. Incidental findings would in case of appearance be discussed with the study team and if need be with the Ethics Committee. Study participation is voluntary and may be revoked without explanation as described above.

